5.4.2 Cytokine release syndrome and macrophage activation syndrome

Given that pembrolizumab will be administered after patients have received CART-19 therapy, the possibility of re-activating CART-19 cells with subsequent development of cytokine release syndrome exists.

Overview and Clinical Manifestations: Patients treated with pembrolizumab who have previously received CART-19 may experience a cytokine release syndrome (CRS), which has correlated with disease response. Clinical manifestations have included high fevers, fatigue, anorexia, nausea, vomiting, headache, rash, hypotension (occasionally requiring pressor support) tachypnea, hypoxia (occasionally requiring ventilator support), delirium and confusion (in several patients), evidence of disseminated intravascular coagulation as well as macrophage activation syndrome (MAS). In some cases CRS, TLS and hypotension have led to acute kidney injury and several patients have required at least transient dialysis. The CRS has been effectively abrogated with anti-cytokine directed therapy including tocilizumab in most patients. As of July 2014, three patients on another CART-19 trial have died of complications related to refractory CRS and intercurrent infections. It is unclear if treating the CRS adversely impacts the anti-tumor response.

Features consistent with MAS or HLH have been observed in patients treated with CART 19, coincident with clinical manifestations of the CRS. MAS appears to be a reaction to immune activation that occurs from the CRS, and therefore should be considered a manifestation of CRS.

Macrophage activation syndrome (MAS) is similar to Hemophagocytic lymphohistiocytosis (HLH); it is a reaction to immune stimulation by infection, autoimmune diseases or other precipitants, but is distinguished from familial or genetically mediated HLH. There are no definitive diagnostic criteria for MAS, but it is typically diagnosed by meeting HLH criteria.

Some but not all features of MAS are typically observed. The clinical syndrome of MAS is characterized by high grade non-remitting fever, cytopenias affecting at least two of three lineages, and hepatosplenomegaly. It is associated with biochemical abnormalities, such as high circulating levels of serum ferritin, soluble interleukin-2 receptor (sCD25), and triglycerides, together with a decrease of

This document is confidential and the property of the University of Pennsylvania. No part of it may be transmitted, reproduced, published, or used by other persons without prior written authorization from the regulatory sponsor.

circulating NK activity. Other findings include variable levels of transaminases up to signs of acute liver failure and coagulopathy with findings consistent with DIC. A pathologic feature of MAS is the presence of hemophagocytic CD163+ macrophages (HPC) in bone marrow or lymph-node aspirates.

Diagnosis of HLH is based on the fulfillment of criteria established in 2004¹⁰¹ for HLH associated with autosomal recessive disorders (familial HLH, fHLH).

A diagnosis of non-familial HLH/MAS is made by having 5/8 criteria:

- Fever
- Splenomegaly
- Cytopenias (affecting 2 or more lineages in the peripheral blood; hemoglobin <9 g/dL, platelets $<100,000/\mu\text{L}$, Absolute neutrophil count $<1000/\mu\text{L}$)
- Fasting triglycerides >265 mg/dL , Fibrinogen <1.5 g/L
- Hemophagocytosis in bone marrow or spleen or lymph nodes
- Low or absent NK-cell activity
- Ferritin >500 g/L
- Soluble CD25R >2400 U/L

Supportive clinical criteria include neurologic symptoms and cerebrospinal fluid pleocytosis, conjugated hyperbilirubinemia, and transaminitis, hypoalbuminemia and hyponatremia. Typically, high fevers, cytopenias, and when performed, hemophagocytosis in the bone marrow is observed (though marrow specimens at the time of the reaction are not often taken). Soluble CD25R and NK cell activity are not standard tests, though samples are taken for retrospective CD25R analysis. Therefore, patients may not meet strict definition of HLH/MAS, but given the constellation of findings, and the consistent dramatic elevation in Ferritin, this is indeed the reaction associated with the CRS.

This document is confidential and the property of the University of Pennsylvania. No part of it may be transmitted, reproduced, published, or used by other persons without prior written authorization from the regulatory sponsor.

At this time it is still unknown whether CRS/MAS is beneficial or harmful to the antitumor response. Research monitoring data showed that IL6 levels were extraordinarily high during the CRS, prompting us to use an anti-IL6 receptor antibody tocilizumab to treat the CRS/MAS. The majority of patients treated with tocilizumab for CRS and MAS had rapid (within hours) resolution of dramatic fevers, and continuous improvement in hypotension and hypoxia over hours to several days, and showed improvement in biochemical evidence of CRS and MAS within 48 hours. Adult patients were treated with tocilizumab 4mg/kg or 8mg/kg. It is unclear if early treatment will negate the antitumor response. Treatment and timing of treatment of this toxicity will be at the discretion of the patient's physician and the study principal investigator, and occur in the setting of hemodynamic instability.

Management of cytokine release syndrome

Some patients who have responded to CART-19 cells have experienced a CRS. Cytokine production is required for the activation, expansion and cytolytic function of T cells and for CART-19 T cells. Therefore some degree of CRS may be a desired clinical outcome. Premature or early intervention with anti-cytokine therapy may therefore abrogate the anti-tumor efficacy of CART-19. Subsequent to this experience, selective tocilizumab (an anti-IL6-receptor antibody) therapy has been utilized (described below) with effective toxicity management and successful ongoing CART-19 T cell expansion in patients. Please note, steroids or other immunosuppressant drugs should **NOT** be used as pre-medication for pembrolizumab but may be considered in the management of CRS.

The moderate to severe cases of CRS observed required intervention with tocilizumab, with or without high dose corticosteroids, between 2 and 9 days after T cell infusion. This resulted in rapid reversal of the high persistent fevers associated with CRS in most but not all patients.

Given the dramatic clinical improvement of most patients treated with anti-cytokine therapy, patients with moderate to severe cytokine toxicities should be first managed with administration of tocilizumab.

Tocilizumab should be used as a weight-based dose of 8 mg/kg at the time of hemodynamic instability. This management approach is designed to avoid life-threatening toxicities, while attempting to allow the CART-19 cells to establish a proliferative phase that appears to correlate with anti-tumor efficacy. Thus, the timing of the tocilizumab should be individualized, in close consultation with the Principal Investigator and/or expert consultants for the trial. Steroids have not always been effective in this setting and may not be

This document is confidential and the property of the University of Pennsylvania. No part of it may be transmitted, reproduced, published, or used by other persons without prior written authorization from the regulatory sponsor.

necessary given the rapid response to tocilizumab. Because steroids will interfere with CART-19 function and efficacy, if used, they should be rapidly tapered.

Upon developing the prodrome of high-persistent fevers following CART-19 infusion, patients should then be followed closely. Infection and tumor lysis syndrome work up should be immediately undertaken. The pharmacy should be notified of the potential need for tocilizumab. Patient management in an intensive care unit may be required and the timing is dependent upon local institutional practice. In addition to supportive care, tocilizumab may be administered in cases of moderate to severe CRS, especially if the patient exhibits any of the following:

- Hemodynamic instability despite intravenous fluid challenges and moderate stable vasopressor support
- Worsening respiratory distress, including pulmonary infiltrates, increasing oxygen requirement including high-flow O₂, and/or need for mechanical ventilation.
- Any other signs or symptoms of rapid deterioration despite medical management

The recommended dosing for tocilizumab is 8 mg/kg i.v. single dose. Not all Grade 4 CRS reactions following CART-19 have been immediately treated with tocilizumab and decisions are, in part, based upon the rapidity of the syndrome onset and underlying patient reserve.

Other anti-cytokine therapies, such as repeat administration of tocilizumab or use of siltuximab or etanercept, may also be considered if the patient does not respond to the initial dose of tocilizumab. If the patient experiences ongoing CRS despite administration of anti-cytokine directed therapies, anti T-cell therapies such as Cytosan, ATG, Campath may be considered.

CRS has been associated with biochemical and physiologic abnormalities consistent with MAS. Moderate to extreme elevations in serum C-reactive protein (CRP) and ferritin have been seen with CART-19 associated CRS, however the magnitude and kinetics vary greatly between individual patients. CRS management decisions should be based upon clinical signs and symptoms and response to interventions, not these laboratory values *per se*.

This document is confidential and the property of the University of Pennsylvania. No part of it may be transmitted, reproduced, published, or used by other persons without prior written authorization from the regulatory sponsor.

CTCAE grading of CRS relates to its occurrence with acute infusional toxicities, whereas the CRS associated with CART-19 therapy is not acute, but rather delayed. Refer to Section 7.3.3 for modified definitions of grading of CART-19 delayed CRS events.

5.5 Diet/Activity/Other Considerations

5.5.1 Diet

Subjects should maintain a normal diet unless modifications are required to manage an AE such as diarrhea, nausea or vomiting.

5.5.2 Contraception

Pembrolizumab may have adverse effects on a fetus in utero. Furthermore, it is not known if pembrolizumab has transient adverse effects on the composition of sperm. Non-pregnant, non-breast-feeding women may be enrolled if they are willing to use 2 methods of birth control or are considered highly unlikely to conceive. Highly unlikely to conceive is defined as 1) surgically sterilized, or 2) postmenopausal (a woman who is ≥ 45 years of age and has not had menses for greater than 1 year will be considered postmenopausal), or 3) not heterosexually active for the duration of the study. The two birth control methods can be either two barrier methods or a barrier method plus a hormonal method to prevent pregnancy. Subjects should start using birth control from study Visit 1 throughout the study period up to 120 days after the last dose of study therapy.

The following are considered adequate barrier methods of contraception: diaphragm, condom (by the partner), copper intrauterine device, sponge, or spermicide. Appropriate hormonal contraceptives will include any registered and marketed contraceptive agent that contains an estrogen and/or a progestational agent (including oral, subcutaneous, intrauterine, or intramuscular agents).

Subjects should be informed that taking the study medication may involve unknown risks to the fetus (unborn baby) if pregnancy were to occur during the study. In order to participate in the study they must adhere to the contraception requirement (described above) for the duration of the study and during the follow-up period defined in section 7.2.2-Reporting of Pregnancy and Lactation to the Sponsor and to Merck. If there is any question that a subject will not reliably comply with the requirements for contraception, that subject should not be entered into the study.

This document is confidential and the property of the University of Pennsylvania. No part of it may be transmitted, reproduced, published, or used by other persons without prior written authorization from the regulatory sponsor.

5.5.3 Use in Pregnancy

If a subject inadvertently becomes pregnant while on treatment with pembrolizumab, the subject will immediately be removed from the study. The site will contact the subject at least monthly and document the subject's status until the pregnancy has been completed or terminated. The outcome of the pregnancy will be reported to the Sponsor and to Merck without delay and within 24 hours to the Sponsor and within 2 working days to Merck if the outcome is a serious adverse experience (e.g., death, abortion, congenital anomaly, or other disabling or life-threatening complication to the mother or newborn).

The study investigator will make every effort to obtain permission to follow the outcome of the pregnancy and report the condition of the fetus or newborn to the Sponsor. If a male subject impregnates his female partner the study personnel at the site must be informed immediately and the pregnancy reported to the Sponsor and to Merck and followed as described above and in Section 7.2.2.

5.5.4 Use in Nursing Women

It is unknown whether pembrolizumab is excreted in human milk. Since many drugs are excreted in human milk, and because of the potential for serious adverse reactions in the nursing infant, subjects who are breast-feeding are not eligible for enrollment.

5.6 Subject Withdrawal/Discontinuation Criteria

Subjects may withdraw consent at any time for any reason or be dropped from the trial at the discretion of the investigator should any untoward effect occur. In addition, a subject may be withdrawn by the investigator or the Sponsor if enrollment into the trial is inappropriate, the trial plan is violated, or for administrative and/or other safety reasons. Specific details regarding discontinuation or withdrawal are provided in Section 7.1.3– Other Procedures.

A subject must be discontinued from the trial for any of the following reasons:

- The subject or legal representative (such as a parent or legal guardian) withdraws consent.
- Confirmed radiographic disease progression

This document is confidential and the property of the University of Pennsylvania. No part of it may be transmitted, reproduced, published, or used by other persons without prior written authorization from the regulatory sponsor.

Note: For unconfirmed radiographic disease progression, if a biopsy is felt clinically necessary, patients may continue pembrolizumab until progression is biopsy confirmed.

Progressive disease (PD): Immunotherapeutic agents such as pembrolizumab may produce antitumor effects by potentiating endogenous cancer-specific immune responses. The response patterns with immunotherapy may extend beyond the typical course of responses seen with cytotoxic agents and can manifest as a clinical response preceded by initial increase in tumor burden, the appearance of new lesions, or a mixed response with some enlarging lesions while other lesions are regressing. Therefore, if the investigator feels the patient has clinical benefit, subjects may continue pembrolizumab until progression is 1) confirmed at follow-up imaging at next response assessment unless clinically indicated to perform sooner and 2) found to have progressive disease at a subsequent imaging evaluation.

Evidence of PD will be based on a comparison with baseline (or nadir) scans or other evaluations.

Subjects with PD on imaging should be managed as follows:

Subjects will be permitted to continue pembrolizumab beyond first confirmed progressive disease as measured by the 2007 Revised response criteria for malignant lymphoma as long as the following are true:

- Investigator assessed clinical benefit

AND

- Subject is tolerating pembrolizumab

Subjects that meet the above criteria and continue pembrolizumab must discontinue pembrolizumab upon the next documented event of PD. The assessment of clinical benefit should be balanced by clinical judgment as to whether the subject is clinically deteriorating and unlikely to receive any benefit from continued treatment. The decision to continue treatment should be discussed with the Principal Investigator and Medical Monitor and documented in the study records.

This document is confidential and the property of the University of Pennsylvania. No part of it may be transmitted, reproduced, published, or used by other persons without prior written authorization from the regulatory sponsor.

- Unacceptable adverse experiences as described in Section 5.2.1.2
- Intercurrent illness that prevents further administration of treatment
- Investigator's decision to withdraw the subject
- The subject has a confirmed positive serum pregnancy test
- Noncompliance with trial treatment or procedure requirements
- The subject is lost to follow-up
- Completed 12 months of uninterrupted treatment with pembrolizumab or 18 administrations of study medication, whichever is later.

Note: 12 months of study medication is calculated from the date of first dose. Subjects who stop pembrolizumab after 12 months may be eligible for up to one year of additional study treatment if they progress after stopping study treatment provided they meet the requirements detailed in Section 7.1.3.5

- Administrative reasons

The End of Treatment and Follow-up visit procedures are listed in Section 7.1.3 Visit Requirements. After the end of treatment, each subject will be followed for 30 days for adverse event monitoring (serious adverse events will be collected for 90 days after the end of treatment as described in Section 7.2.3.1).

5.7 Second Course

Additional details are provided in Section 7.1.3.5.

This document is confidential and the property of the University of Pennsylvania. No part of it may be transmitted, reproduced, published, or used by other persons without prior written authorization from the regulatory sponsor.

5.8 Subject Replacement Strategy

1. If a subject is enrolled, but does not receive any doses of pembrolizumab, they may be replaced, to allow for a total of 12 subjects treated with pembrolizumab who are assessed for response rate
2. If a subject receives one dose of pembrolizumab but is removed from study for a reason aside from toxicity prior to receiving 4 doses of pembrolizumab, this patient may be replaced to allow for a total of 12 subjects treated with pembrolizumab who are assessed for response rate. Patients removed prior to 3 months who have not experienced toxicity will be included for efficacy analyses but will not be included in toxicity analysis.

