1.0 TRIAL SUMMARY

Title	Phase I/II study of pembrolizumab in patients failing to respond to or relapsing after anti-CD19 chimeric antigen receptor modified T cell therapy for relapsed or refractory CD19+ lymphomas
Abbreviated Title	Pembrolizumab after CTL019/CTL119 for relapsed/refractory CD19+ lymphomas
Trial Phase	Phase I / II
Clinical Indication	Relapsed / refractory CD19+ B cell lymphomas after CTL019/CTL119
Trial Type	Investigator-initiated
Type of control	None. Enrollment will be offered to subjects with an unmet medical need, which is no available effective, standard therapy for relapsed / refractory CD19+ lymphomas
Route of administration	Intravenous
Trial drug, dose, route, regimen	Pembrolizumab (Keytruda [®]) 200mg fixed dose IV every 3 weeks
Trial Blinding	None
Treatment Groups	Single group
Number of trial subjects	12 evaluable subjects
Estimated enrollment period	12 months (approximately January 2016-January 2017)
Estimated duration of trial	36 months (approximately January 2016-January 2019)
Duration of Participation	24 months (12 months treatment + 12 months follow-up)
Objectives	
Primary Endpoints:
 
 1. Determine safety of pembrolizumab after CTL019/CTL119. This endpoint will be met if $\leq 30\%$ of patients develop toxicity resulting discontinuation of pembrolizumab. 2. Determine efficacy of pembrolizumab after CTL019/CTL119. This endpoint will be met if the ORR at 3 months is $\geq 35\%$.
Statistical methodology	
Primary Endpoints:
 
 1. Safety endpoint will be assessed using a Bayesian monitoring rule to ensure probability of a patient developing toxicity resulting in discontinuation of pembrolizumab $\leq 30\%$ 
Secondary Endpoints:
 
 1. ORR will be assessed using a one-sided binomial test 2. PFS, EFS, RD, and OS will be assessed using Kaplan Maier survival analysis. PFS after pembrolizumab will be compared to PFS after CTL019/CTL119 using a log rank test.

This document is confidential and the property of the University of Pennsylvania. No part of it may be transmitted, reproduced, published, or used by other persons without prior written authorization from the regulatory sponsor.

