8.1.2 Secondary Objectives & Hypotheses

Any patient who receives at least one dose of pembrolizumab will be included in efficacy analyses.

(1) Objective: To describe the overall response rate (ORR) to pembrolizumab in patients failing to respond to or relapsing after anti-CD19 chimeric antigen receptor modified T cell therapy for relapsed or refractory CD19+ lymphomas.

Methodology: For efficacy, a sample size of 12 patients achieves an 80% power to detect a difference (P1 0.35 – P0 0.05) of 0.30 using a one-sided binomial test for ORR. The target of significance level is 0.05. This response rate prediction of 35% is based on the reported 28% response rate reported for nivolumab, another anti-PD1 blocking antibody, in patients with B cell lymphoma. This also assumes that a 5% response rate would be seen if pembrolizumab does not have efficacy in this population. If the response rate is 3 or more, the hypothesis that the ORR is ≤ 0.05 is rejected. If the number of responses is 2 or less, the hypothesis that ORR is ≥ 0.35 .

Hypothesis: The response rate after pembrolizumab will be 3 or more, allowing us to reject the null hypothesis that pembrolizumab after CTL019/CTL119 has an ORR ≤ 0.05

(2) Objective: To describe the clinical efficacy of pembrolizumab, including progression-free survival, disease-free survival, event-free survival, response duration, and overall survival (Cheson, 2007) in patients failing to respond to or relapsing after anti-CD19 chimeric antigen receptor modified T cell therapy for relapsed or refractory CD19+ lymphomas. Efficacy comparisons will be made with both most recent prior therapy as well as with CTL019/CTL119.

Methodology: Kaplan Meier survival analysis will be used to estimate progression-free survival, event-free survival, response duration, and overall survival. For patients with initial responses to both CTL 019 and pembrolizumab, progression-free survival, event-free survival, and response duration, patients' response to CTL 019 therapy will be compared to their response to pembrolizumab using the log-rank test, with $p \leq 0.05$ considered statistically significant.

Hypothesis: Pembrolizumab will enhance the efficacy of CTL019/CTL119 in patients failing to respond to or relapsing after chimeric antigen receptor modified T cell therapy for relapsed or refractory CD19+ lymphomas.

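### Does replacing dosed patients undermine the response-rate rule of 3 or more, which was derived for 12 patients?

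*Combined protocol and SAP*

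**What the plan says.** The efficacy design is in section 8.1.2. It states that "a sample size of 12 patients achieves an 80% power to detect a difference" between a null ORR of 0.05 and an alternative of 0.35, using a one-sided binomial test. "The target of significance level is 0.05", and the decision rule is "If the response rate is 3 or more, the hypothesis that the ORR is ≤ 0.05 is rejected", where the 3 is plainly a count of responders. The section opens with its analysis set: "Any patient who receives at least one dose of pembrolizumab will be included in efficacy analyses".

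Section 5.8, item 2, allows replacement of a patient who has been dosed but is removed before four doses for a non-toxicity reason, and gives the purpose: "this patient may be replaced to allow for a total of 12 subjects treated with pembrolizumab who are assessed for response rate". It sets no limit on replacements. Its next sentence says that patients removed before 3 months without toxicity "will be included for efficacy analyses but will not be included in toxicity analysis".

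The Trial Summary (1.0) gives the trial size as "12 evaluable subjects", and section 2.1 anticipates 12 patients in total. The Trial Summary also carries a separate efficacy criterion, "This endpoint will be met if the ORR at 3 months is" at least 35%.

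**The concern.** Two descriptions of the response-rate population seem to compete. One is everyone who received a dose; the other is a set of 12 who are assessed or evaluable. If dosed patients are replaced without limit and also kept in the analysis, the denominator exceeds 12 while the cut-off stays at 3. A fixed count becomes easier to reach as patients are added, so the chance of wrongly rejecting an ORR of 5% rises and could pass the stated level.

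The choice of denominator could also move the 35% criterion in the Trial Summary: five responders are 5/12 = 41.7%, but 5/15 = 33.3% once three dosed patients have been replaced. And if patients who leave early for progression could drop out of the denominator, the reported ORR would be flattered.

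**Working it through.** **Inputs.** From 8.1.2: N = 12, null rate 0.05, alternative 0.35, one-sided level 0.05, reject at 3 or more. From 5.8: replacement of dosed patients is optional and uncapped. The documents give no response rate for early leavers, so it is treated below as an assumption, q.

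**1. The plan's own figures.** For N patients with response rate p,

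P(X ≥ 3) = 1 − (1−p)^N − N·p·(1−p)^(N−1) − [N(N−1)/2]·p²·(1−p)^(N−2).

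- Error at N = 12, p = 0.05: 1 − 0.5404 − 0.3413 − 0.0988 = 0.0196.
- Power at N = 12, p = 0.35: 1 − 0.0057 − 0.0368 − 0.1088 = 0.8487.
- A cut-off of 2 at N = 12 would have an error of 0.1184, so 3 is correct.
- At N = 11 the power is 0.79987, so 12 is the smallest sample size that reaches 80%.

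The design reproduces.

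**2. The fixed count of 3 when everyone dosed responds at 5%.**

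| Patients dosed | Replaced | P(X ≥ 3) |
|---|---|---|
| 12 | 0 | 1.96% |
| 13 | 1 | 2.45% |
| 14 | 2 | 3.01% |
| 15 | 3 | 3.62% |
| 16 | 4 | 4.29% |
| 17 | 5 | 5.03% |
| 20 | 8 | 7.55% |

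The first excess, at 17, is 0.025 percentage points (5.025% against 5%).

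**3. Leavers with their own response rate q.** Let the 12 others respond at 5% and the L leavers at q. The error is P(Bin(12, 0.05) + Bin(L, q) ≥ 3).

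| q | L = 5 (N = 17) | L = 8 (N = 20) |
|---|---|---|
| 0 | 1.96% | 1.96% |
| 2.5% | 3.34% | 4.35% |
| 5% | 5.03% | 7.55% |

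The 5% level is passed only if q exceeds about 4.97% with five leavers, or 3.06% with eight.

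**4. The named test at the actual N.** The smallest count with P(X ≥ c) ≤ 0.05 under the null is 3 for every N from 8 to 16, and 4 from 17 to 28. At N = 17 a cut-off of 4 has an error of 0.88% and, if 35% holds in all dosed patients, power of 89.7%.

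If leavers do not respond, adding them or leaving them out does not alter the number of responders. Because the cut-off is 3 throughout 8 to 16, the test decision is then the same under either denominator with up to four replacements.

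**5. Which denominator the text supports.** The section that contains the ORR test opens by including every dosed patient, and 5.8 says the same of patients removed early. No passage excludes a dosed patient from the ORR. The mentions of 12 in 1.0, 2.1 and 5.8 say how many patients to accrue and why replacement is allowed; none of them defines an analysis set.

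**The case for a change.** The best case for a change is that replacement is foreseeable. The fourth three-weekly dose falls at about week 9, before the week-12 response scan in 6.3. Confirmed progression is a listed reason for discontinuation in 5.6, and the patients have relapsed or refractory disease. As written, a patient removed early for progression may be replaced. Section 5.8 speaks of subjects assessed for response rate, and ORR is a response rate, so a reader could take 12 as its denominator and drop early failures. One sentence would close the door before results are seen.

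Part of this stands. The wording about 12 sits awkwardly beside an all-dosed set, replacement is uncapped, 8.1.2 gives no cut-off for another sample size, and nothing says how a dosed patient without an assessment is scored. But the risk of dropping early failures is the one the two inclusion sentences already rule out. The same feature also weakens the error-rate argument: patients who leave for progression are non-responders, and non-responders do not raise the count. Section 6.3 does call for imaging at discontinuation in many cases, so a response in a leaver is possible, but a rate close to the full null rate is a strong assumption for this group.

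The 5/12 against 5/15 example needs the denominator that the text does not support. It also rests on a separate mismatch that exists with no replacement at all: 3/12 = 25% and 4/12 = 33.3% both reject the null under 8.1.2 yet miss 35%. At a true ORR of 35%, one of those two results occurs about 43% of the time. Settling the denominator would not resolve that.

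**Conclusion.** The concern does not call for a change. Followed as written, the plan tests the ORR in all dosed patients with a one-sided binomial test at 0.05, and the count of 3 is the design cut-off for the planned 12. That cut-off remains the right one with up to four replaced patients. Beyond that, an analyst applying the named test at the actual number dosed would use 4 responses, and would ordinarily count a dosed patient with no documented response as a non-responder.

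An error rate above 5% needs three things together: at least five optional replacements in a trial that anticipates 12 patients, leavers responding at about the null rate, and literal use of 3 at a sample size it was not stated for. Even then the excess at 17 patients is 0.025 percentage points. It would be larger at 20 (7.55% in total), but eight replacements is not a realistic prospect here. What remains is missing detail that analysts fill sensibly, with no effect on any realistic result. The judgement rests on reading the references to 12 as an accrual target and on early leavers responding rarely, if at all.
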